9.4 Other Endpoints/Assessments

9.4.1 Hospital-free Days up to Day 90

Hospital stay is defined (from the eCRF) as "Other acute care hospital" or "Still in trial hospital"

Hospital-free Days up to Day 90 will be defined and analyzed in a similar manner as the primary endpoint, with the van Elteren test stratified by need for ventilation (Yes/No), time from onset of shock to start of treatment (< or \ge 6 hours), and norepinephrine/noradrenaline requirement at baseline (< or \ge 30 µg/min) and baseline creatinine (< or \ge 150 µmol/L).

9.4.2 Hospital Length of Stay up to Day 90

Hospital length of stay is defined as the cumulative periods spent in hospital ("Other acute care hospital" or "Still in trial hospital") from start of IMP to 90 days after.

For patients withdrawn or dying while still in hospital up to Day 90, the duration will be based on the data available up until the time of withdrawal or death.

Page 39 of 80

Hospital length of stay will be analyzed between treatment groups using the permutation test specified in Section 9.3.1.3 stratified by the combination of time from onset of shock to start of treatment (< or \ge 6 hours), baseline creatinine (< or \ge 150 μ mol/L), norepinephrine/noradrenaline requirement at baseline (< or \ge 30 μ g/min) and need for ventilation (Yes/No).

9.4.3 Patient Residence at Day 30, Day 60, Day 90, and Day 180

Patient location at Day 30, 60, 90 and 180 will be summarized by treatment arm (including pooled active treatment arms). Baseline is the timing prior to acute admission.

Shift tables will be presented at each time point to assess whether patients have returned to their location at enrollment. There will be no imputations of missing values.

9.4.4 Mean Arterial Pressure, Until ICU Discharge (for a Maximum of 7 Days)

Mean arterial pressure will be tabulated by treatment arm (including pooled active treatment arms) and presented graphically (at pre-specified time points, i.e. not when NE/NA infusion changes, and only until ICU discharge/day 7) for both MAP alone, and the difference from MAP to target MAP (which is 65, unless the investigator judges it to be otherwise). There will be no imputations of missing values.

MAP will be displayed both for MAP measurements taken while patients are in and out of septic shock, i.e. while patients are on and off IMP/vasopressors (as defined for the primary endpoint).

Difference to target MAP will only be displayed for MAP measurements taken while patients are in septic shock.

9.4.5 Norepinephrine/Noradrenaline and Other Vasopressor Doses

The cumulative dose of norepinephrine/noradrenaline administered (adjusted for baseline weight) will be derived as an area under the curve (AUC) of the actual norepinephrine doses and actual time points (although analysed at planned time points). Linear interpolation will be used to derive the AUC (taking into account that only patients enrolled before noon will have a measurement at 36 hours after IMP start). Patients dead or withdrawn will be set to missing. The cumulative doses ($\mu g/kg$) will be compared between treatment arms using a repeated measures ANCOVA model with baseline dose of norepinephrine/noradrenaline ($\mu g/kg/min$) as covariate, treatment, time and treatment by time interaction as factors, baseline dose by time interaction, and patient as the experimental unit. Estimated treatment differences (to placebo) along with a 95% confidence interval will be presented.

If a patient has missing values and the patient is still in the trial (not dead or withdrawn) it will be assumed that the specific vasopressor was not given and a value of zero will be imputed, unless there is an interval in the timing log covering the exact time point (8 AM and 8 PM is the assumed time point for missing morning and evening collection time points). In that case LOCF will be used, but only within the time interval.

Date: 20 Nov 2017 E-Statistical Analysis Plan-17877; Ver.9.0 Supersedes: Ver. 8.0

Page 40 of 80

The mean dose and cumulative dose administered will be tabulated by treatment arm (including pooled active treatment arms), and presented graphically.

To assess the time needed to wean the patients off norepinephrine, the percentage change from baseline in norepinephrine dose ($\mu g/kg/min$) will be compared between treatment arms using a repeated measures ANCOVA model with baseline dose of norepinephrine/noradrenaline ($\mu g/kg/min$) as covariate, treatment, time and treatment by time interaction as factors, baseline dose by time interaction, and patient as the experimental unit. Estimated treatment differences (to placebo) along with a 95% confidence interval will be presented at 1, 3, 6, 12 and 24 hours after start of IMP treatment.

The same analyses (adjusted for baseline dose of norepinephrine/noradrenaline ($\mu g/kg/min$)) will be performed for the following endpoints:

- Catecholamines (defined as the sum of doses of norepinephrine/noradrenaline, epinephrine/adrenaline, dopamine, and phenylephrine) (ug/kg)
- Catecholamines excluding norepinephrine/noradrenaline (ug/kg)
- Vasopressin (U/kg)

For the sum of catecholamine doses we define 100 µg dopamine, 1 µg epinephrine, and 2.2 µg phenylephrine all equivalent to 1 µg norepinephrine.

Also, the number of patients receiving terlipressin will be summarised.

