7	Nov 9 - 2017	Additional analyses to MAP analyses. Analysis for duration of septic shock changed from ANCOVA to negative binomial (as blinded data suggests a better fit) with permutation test as backup in case model assumptions do not hold. Analyses for duration of ventilation and duration of RRT changed from ANCOVA to zero inflated negative binomial (as blinded data suggests a better fit) also with permutation test as backup in case model assumptions do not hold. Analysis for ICU length of stay and hospital length of stay changed from ANCOVA to permutation test (as blinded data suggested a non-parametric model). Covariates were dichotomized accordingly. Appendix 4 removed as no longer needed. Appendix 3 updated with variance correction for difference in PVFDs Analyses in 9.4.8, 9.4.9, and 9.4.10 will not be repeated for the selected arm only and data from part 2 only, as they are measured on a subset of patients, probably only in part 1. A "time" by "baseline value" interaction term has been added to the repeated ANCOVA analyses in 9.3.1.5, 9.3.3.1, 9.3.4.1, 9.3.4.2, and 9.4.5 as it is likely that the trajectory over time for each patient will depend on the baseline value. The supportive competing risk and Kaplan-Meier graphs for duration of RRT has been taken out as it makes no sense since RRT durations are short and repetitive. It is more meaningful to just look at 90 day mortality. For the remaining 'duration' endpoints withdrawal rates has been added to the competing risk and Kaplan-Meier graphs. As this is a superiority trial, the PP analysis will only be performed for the primary endpoint, and hence not performed for secondary as previously stated.	Version 6

Date: 20 Nov 2017 E-Statistical Analysis Plan-17877; Ver.9.0 Supersedes: Ver. 8.0 Page 5 of 80

		Only major protocol deviations will be listed. Adverse events graphs added to output. Fluid balance analyses updated. Analyses for norepinephrine/noradrenaline and other vasopressor doses updated. Forest plots added for incidence of RRT (section 9.3.1.8) and mortality (section 9.3.2.3).	
8	Nov 9 - 2017	Format change only. No content was changed	Version 7
9	Nov 20 - 2017	Format change only. No content was changed	Version 8

Page 6 of 80

Signed agreement on Statistical Analysis Plan

TABLE OF CONTENTS

1	Intro	ductionduction	10			
	1.1	Definitions/ Abbreviations	10			
		1.1.1 Definition of Terms	10			
		1.1.2 Abbreviations	10			
2	Trial	Objectives and Endpoints	12			
	2.1	Objectives	12			

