- Dosing errors expected to significantly impact efficacy
- More than 16 hours from onset of vasopressor treatment to start of IMP
- Failed to receive a continuous infusion of norepinephrine/noradrenaline base greater than 4.5 ug/min for at least one hour or received less than 4.5 ug/min of norepinephrine/noradrenaline base at start of IMP infusion
- Violation of exclusion criteria 2: Primary cause of hypotension not due to sepsis (e.g., major trauma including traumatic brain injury, hemorrhage, burns, or congestive heart failure/cardiogenic shock)
- Violation of exclusion criteria 6: Chronic mechanical ventilation for any reason OR severe chronic obstructive pulmonary disease (COPD) requiring either continuous daily oxygen use during the preceding 30 days or mechanical ventilation (for acute exacerbation of COPD) during the preceding 30 days
- Violation of exclusion criteria 9: Decision to limit full care taken before obtaining informed consent
- Violation of exclusion criteria 10: Use of vasopressin in the past 12 hours prior to start of IMP infusion or use of terlipressin within 7 days prior to start of IMP infusion
- Violation of exclusion criteria 12: Prior use of an investigational medicinal product within the last month OR planned or concurrent participation in a clinical trial for any investigational drug or investigational device

Furthermore, any other major protocol violations, such as serious unforeseen violations deemed to invalidate the data and affect the conclusions of the study will lead to exclusion of data from the PP analysis set.

Major protocol deviations will lead to exclusion of data from the PP analysis, while data will not be excluded because of minor protocol deviations. The list of major protocol deviations will be detailed and documented in the clean file document prior to database release.

All major protocol deviations will be listed in patient data listings.

Page 20 of 80

6 Analysis sets

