9.3.1.4 Duration of Mechanical Ventilation up to Day 30

Duration of mechanical ventilation is defined as the cumulative periods (>1 hour) from start of IMP until Day 30, on mechanical ventilation. Mechanical ventilation during - and up to three hours after - surgery / procedure is exempt from this rule.

For patients withdrawn or dying while still on mechanical ventilation, the duration will be based on the data available up until the time of withdrawal or death.

Duration of mechanical ventilation will be analyzed separately for survivors, non-survivors (within the first 30 days) and overall using a zero inflated negative binomial model with time from onset of shock to start of treatment, and norepinephrine/noradrenaline requirement at baseline (μ g/kg/min) as covariates, and treatment and need for ventilation as factors. As duration of ventilation is derived with two decimal points (with values in the range of 0.00, 0.01, ..., 90.00), duration of ventilation

Page 32 of 80

will be transformed (for model stability) to integer values (with values in the range of 0, 1, ..., 9000) by multiplying with 100. Treatment estimates will be back transformed.

In case the model assumptions for duration of ventilation does not hold, the permutation test specified in Section 9.3.1.3 will be used including an analysis of the expected proportion of patients with 0 duration, and estimates of the duration for those with a positive duration.

9.3.1.5 Daily Overall and Individual Organ (Cardiovascular, Respiratory, Renal, Hepatic, Coagulation) Scores using the Modified Sequential Organ Failure Assessment (SOFA) Scores Until ICU Discharge

Last observation carried forward (LOCF) will be used for missing SOFA scores on Days 2-7. No LOCF for Day 1 (as previous value is baseline). Patients dying will be imputed with a worst possible outcome, i.e. a value of 4 for each individual SOFA score.

Daily overall (modified) and individual SOFA scores will be compared between treatment arms up until Day 7 using a repeated measures ANCOVA model with baseline SOFA score as covariate, treatment, time and treatment by time interaction as factors, baseline SOFA score by time interaction, and patient as the experimental unit. The estimated treatment difference (to placebo) with a 95% confidence interval will be presented.

Furthermore, daily overall and individual SOFA scores will be tabulated by treatment arm (including pooled active treatment arms).

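### Section 9.4.5 adjusts the dose of catecholamines other than norepinephrine only for baseline norepinephrine and omits that outcome's own baseline; adding it can only help precision, by an amount the SAP does not let one state

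*SAP*

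**What the plan says.** Section 9.4.5 first analyses cumulative norepinephrine dose by repeated-measures ANCOVA. The covariate is baseline norepinephrine dose (µg/kg/min), and the model has treatment, time, treatment by time, and "baseline dose by time interaction, and patient as the experimental unit". A similar model is given for percentage change from baseline.

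The section then extends this: "The same analyses (adjusted for baseline dose of norepinephrine/noradrenaline" will be performed for three more outcomes:

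- total catecholamines: "Catecholamines (defined as the sum of doses of norepinephrine/noradrenaline, epinephrine/adrenaline, dopamine, and phenylephrine";
- "Catecholamines excluding norepinephrine/noradrenaline (ug/kg";
- vasopressin.

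Other catecholamines are converted to norepinephrine equivalents for the sum. No baseline dose other than norepinephrine enters any of the three models.

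The change log for version 7 names 9.4.5 among the sections given a baseline-by-time term, "as it is likely that the trajectory over time for each patient will depend on the baseline value".

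**The concern.** In the norepinephrine model the covariate is the outcome's own baseline. Carried over to the non-norepinephrine catecholamines, the same covariate is the one drug that the outcome excludes. A patient already on epinephrine, dopamine or phenylephrine when IMP starts is likely to accumulate more of it, and the model cannot use that information. The baseline-by-time term then does not contain the value that the change log gives as its reason.

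This outcome shows whether selepressin reduces the use of other catecholamines or shifts use towards them. It is likely to be sparse and skewed, so a few patients already on such a drug could carry much of the variance. Randomisation is stratified by norepinephrine requirement but not by use of other catecholamines. At stake is a wider interval than the data may allow.

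**Working it through.** **1. Which baseline each repeated-measures ANCOVA uses**

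| Section | Outcome | Baseline covariate |
|---|---|---|
| 9.3.1.5 | SOFA | own ("using a repeated measures ANCOVA model with baseline SOFA score as covariate") |
| 9.3.3.1 | EQ-5D index, VAS | own |
| 9.3.4.1 | fluid balance, fluid overload | own |
| 9.3.4.2 | urinary output | own |
| 9.4.11 | creatinine clearance | own |
| Addendum 2.5 | PaO2/FiO2 | own |
| 9.4.5 | norepinephrine | own |
| 9.4.5 | non-norepinephrine catecholamines | norepinephrine only |

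No reason is given for the last row.

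**2. Can the own baseline vary between patients?** Section 5 expects a norepinephrine infusion at the start: a patient who "Failed to receive a continuous infusion of norepinephrine/noradrenaline base greater than 4.5 ug/min for at least one hour" leaves the per-protocol set. For vasopressin an exclusion criterion ("Use of vasopressin in the past 12 hours prior to start of IMP infusion") makes the own baseline about zero. None of the violations listed in Section 5 covers epinephrine, dopamine or phenylephrine, so their baseline can be non-zero.

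**3. Formula.** The SAP gives no precision figure for these outcomes, so there is none to reproduce. Let r_NE and r_own be the correlations of the outcome with baseline norepinephrine and with its own baseline. In large samples the variance of the treatment effect, relative to the SAP's model, is:

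- replacing norepinephrine by the own baseline: (1 − r_own²)/(1 − r_NE²);
- adding the own baseline: (1 − R²_both)/(1 − r_NE²).

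R²_both is at least r_own² and at least r_NE². The second ratio therefore never exceeds 1 and never exceeds the first. CI width scales with its square root.

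With r_NE = 0, r_own of 0.1, 0.2, 0.3, 0.5 and 0.7 gives 1 − r_own² = 0.99, 0.96, 0.91, 0.75 and 0.51. Square roots are 0.995, 0.980, 0.954, 0.866 and 0.714, so intervals are 0.5%, 2%, 5%, 13% and 29% narrower.

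**4. Illustration over the infusion period; every input is assumed.** 400,000 simulated patients per scenario; log-normal doses; 5% or 15% start another catecholamine later; exponential durations (mean 1.5 days, norepinephrine 2 days); use either unrelated or related to norepinephrine dose. Ratios are for replacement, so they understate the gain from adding wherever the two differ.

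| On another catecholamine at baseline | Variance ratio | CI narrower (1 − √ratio) |
|---|---|---|
| 0% | 1.00-1.01 (adding: no change) | 0% |
| 2% | 0.85-0.94 | 3-8% |
| 5% | 0.76-0.88 | 6-13% |
| 10% | 0.68-0.81 | 10-18% |
| 20% | 0.62-0.75 | 14-21% |

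**5. Illustration at 24 hours, own baseline added.** Assuming 5-20% on such a drug at baseline and 5-10% new starters, R² is 2-4% with norepinephrine alone and 27-52% with both. The simulated SE ratio is 0.71-0.87; at the upper end, √((1 − 0.52)/(1 − 0.04)) = √0.50 = 0.71. Intervals are 13-29% narrower. Another set of 24-hour assumptions gave 20-32% at 5% usage and 28-37% at 10%. The 24-hour figures thus move strongly with the assumed doses and durations.

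**6. Total catecholamines.** Baseline norepinephrine correlates 0.97-1.00 with the baseline sum. The variance ratio is 0.985-1.00 over the infusion period (√0.985 = 0.992), and the SE ratio at 24 hours is 0.98-0.995. The gain is at most about 2% in SE.

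**The case against.** The strongest reply is that baseline norepinephrine is a deliberate severity covariate. The SAP uses it for septic shock duration, ventilation duration, new organ failures and RRT incidence, none of which has norepinephrine as its own baseline. Adjusting the need for additional drugs for severity of shock is coherent, so a reader should not infer that the adjustment achieves nothing. This stands, and it is why norepinephrine should stay in the model.

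It can also be the better single covariate: with r_NE = 0.3 and r_own = 0.1 or 0.2, replacement gives (1 − 0.01)/(1 − 0.09) = 1.09 or (1 − 0.04)/(1 − 0.09) = 1.05. That argues against replacing it, but not against adding a second covariate.

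A reader might infer that much precision is lost. The documents do not support this, since they give neither baseline usage nor any correlation. Nor do they support a reading of bias: the arms are randomised, the covariate is pre-specified, and chance imbalance is sampling variation that the interval already covers.

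The stakes are modest. The outcome is listed as additional (2.2.5) and lies outside the Hochberg family. Substitution between vasopressors is already handled in the primary endpoint, which counts all of these drugs.

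Finally, availability of the baseline doses is inferred. The repeated analyses include percentage change from baseline, which presupposes such doses, although it is undefined for a patient with a zero baseline. The inference is reasonable but should be confirmed against the case report form.

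**Conclusion.** The point holds as a precision improvement for one outcome. The model for non-norepinephrine catecholamines leaves out the outcome's own baseline, against the SAP's practice elsewhere and against its stated reason for the baseline-by-time term. The gain is nil if nobody is on such a drug at the start. It is roughly 3-30% in CI width under assumed usage of about 2-20%, with 24-hour results able to go somewhat higher under other assumptions. None of these figures can be confirmed from the document.

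The same criticism might be extended to total catecholamines, but there the effect is negligible because norepinephrine dominates the sum. Vasopressin has almost no baseline to adjust for. No primary or key secondary conclusion is affected, and the priority is low.

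**What to change.** In 9.4.5, for catecholamines excluding norepinephrine only, add the baseline dose of the non-norepinephrine catecholamines (norepinephrine equivalents, µg/kg/min) and its interaction with time. Keep baseline norepinephrine dose as a covariate. If the own baseline is left out on purpose, state the reason. Leave the models for total catecholamines and vasopressin as they are.

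The cost is one covariate and its time interaction in one model statement. The degrees of freedom are trivial against the planned 1800 evaluable patients, and still small if early stopping leaves fewer. No new data should be needed, provided the baseline doses were recorded as the change-from-baseline analyses presuppose.

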9.4.6 Pulmonary Function (PaO2/FiO2) (in a subset of patients)

Baseline for PaO2/FiO2 will be the values obtained at the last assessment prior to the first dose of IMP. There will be no imputations of missing values.

Descriptive statistics, i.e., the number of patients with data, mean (standard deviation), median, interquartile range, minimum, and maximum values, will be presented for observed values and change from baseline at each time-point by treatment arm (including pooled active treatment arms).

9.4.7 Arterial Blood Gases and Acid/Base Status (PaO2, PaCO2, pH, SaO2, Bicarbonate, Base Excess), Lactate and Oxygen Saturation in Vena Cava Superior (ScvO2)

Baseline for arterial blood gases, lactate and ScvO2 will be the values obtained at the last assessment prior to the first dose of IMP. There will be no imputations of missing values.

Descriptive statistics, i.e., the number of patients with data, mean (standard deviation), median, interquartile range, minimum, and maximum values, will be presented for observed values and change from baseline at each time-point by treatment arm (including pooled active treatment arms).

Page 41 of 80

9.4.8 Cytokines, ANG-1 and ANG-2 (in a Subset of 100-350 Patients)

Baseline values will be the values obtained at the last assessment prior to the first dose of IMP. There will be no imputations of missing values.

Descriptive statistics, i.e., the number of patients with data, mean (standard deviation), median, minimum, and maximum values, will be presented for observed values and change from baseline at each time-point by treatment arm (including pooled active treatment arms).

These analyses will not be repeated for the selected arm only and data from part 2 only.

9.4.9 EVLW and PPI (in a Subset of 100-350 Patients)

Baseline for EVLW and PPI will be the values obtained at the last assessment prior to the first dose of IMP. There will be no imputations of missing values.

Descriptive statistics, i.e., the number of patients with data, mean (standard deviation), median, interquartile range, minimum, and maximum values, will be presented for observed values and change from baseline at each time-point by treatment arm (including pooled active treatment arms).

These analyses will not be repeated for the selected arm only and data from part 2 only.

9.4.10 Cardiac Output (in a Subset of 100-350 Patients)

Baseline for cardiac output values will be the values obtained at the last assessment prior to the first dose of IMP. There will be no imputations of missing values.

Descriptive statistics, i.e., the number of patients with data, mean (standard deviation), median, interquartile range, minimum, and maximum values, will be presented for observed values and change from baseline at each time-point by treatment arm (including pooled active treatment arms).

These analyses will not be repeated for the selected arm only and data from part 2 only.

9.4.11 Creatinine Clearance

Creatinine clearance is determined by estimated glomular filtration rate (using creatinine, age, and gender as per Cockcroft-Gault).

Cockcroft-Gault equation: creatinine clearance (mL/min) = $((140 - age in years) \times weight (kg)) / creatinine (\mu mol/L)$ for women. For men, multiply result by 1.2.

Creatinine clearance will be analyzed up until day 3 as for fluid balance in Section 9.3.4.1, with baseline creatinine clearance as a covariate, treatment, time and treatment by time interaction as factors, and patient as the experimental unit.

Page 42 of 80

10 Safety

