9.1 General Considerations

All statistical tests will be performed using a two-sided test at a 5% significance level.

If the trial is stopped prematurely due to e.g. futility, the data will be analysed as planned in this statistical analysis plan.

All efficacy endpoints will be analysed for the FAS analysis set, and as a sensitivity the analyses for the primary endpoint will be repeated for the PP population.

Categorical data will be summarised using counts and percentages, while continuous data will be presented using the number of patients (N), mean, standard deviation, median, interquartile range, minimum and maximum. All efficacy endpoints will be listed in patient data listings.

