The number of new organ failures and the number of new organ dysfunctions will be compared between treatment arms using a negative binomial model with age, modified SOFA score and norepinephrine/noradrenaline requirement at baseline ($\mu g/kg/min$) as covariates, and gender and treatment as factors. The estimated treatment difference (to placebo) with a 95% confidence interval will be presented. The 95% confidence interval for the difference in proportions between treatment groups will be constructed using the delta method (see Appendix 4 for details).

Furthermore, incidence of any new organ failure and any new organ dysfunction, and the number of new organ failures and new organ dysfunctions will be tabulated by treatment arm (including pooled active treatment arms).

9.3.1.7 Renal Replacement Therapy (RRT)-free Days up to Day 30 (excluding patients on RRT for chronic renal failure at time of randomisation)

RRT-free Days is defined as for the primary endpoint with free of treatment with any form of renal replacement therapy defined as continuous renal replacement therapy, intermittent hemodialysis or peritoneal dialysis.

RRT-free Days will be analyzed excluding patients on RRT for chronic renal failure at time of randomisation.

RRT-free Days up to Day 30 will be analyzed in a similar manner as the primary endpoint, with the van Elteren test stratified by need for ventilation (Yes/No), time from onset of shock to start of treatment (< or \ge 6 hours), norepinephrine/noradrenaline requirement at baseline (< or \ge 30 μ g/min) and baseline creatinine (< or \ge 150 μ mol/L).

9.3.1.8 Incidence of RRT up to Day 30 (counting patients who die as on RRT and excluding patients on RRT for chronic renal failure at time of randomisation)

RRT is defined as any form of renal replacement therapy defined as continuous renal replacement therapy, intermittent hemodialysis or peritoneal dialysis. In order to ensure that any reduction in incidence of RRT is not caused by an increase in mortality, all patients dying within the 30-day period will be counted as on RRT. For patients withdrawn prior to Day 30, incidence of RRT will be based on the data available up until the time of withdrawal.

Page 34 of 80

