Incidence of RRT will be analysed by a logistic regression model with time from onset of shock to start of treatment, baseline creatinine and norepinephrine/noradrenaline requirement at baseline (µg/kg/min) as covariates, and treatment and need for ventilation as factors. The 95% confidence interval for the difference in proportions between treatment groups will be constructed using the delta method (see Appendix 4 for details). Patients already on RRT for chronic renal failure at time of inclusion will be excluded from the analysis of incidence of RRT.

Non-inferiority will be claimed if the upper limit of the two-sided 95% CI of the adjusted difference in proportions is less than 20% of the estimated incidence of RRT in the placebo group. Superiority can be claimed (5) if the upper limit is less than 0.

I.e., let $\widehat{p_S}$ and $\widehat{p_P}$ be the estimated incidences of RRT in the combined selepressin groups and the placebo group respectively. Non-inferiority will then be claimed if

$$\widehat{p_S} - \widehat{p_P} + 1.96 * \sqrt{var(\widehat{p_S} - \widehat{p_P})} < 0.2 * \widehat{p_P}$$

and superiority will be claimed if

$$\widehat{p_S} - \widehat{p_P} + 1.96 * \sqrt{var(\widehat{p_S} - \widehat{p_P})} < 0$$

A forest plot including the non-inferiority tests for all analyses will be presented.

Furthermore, incidence of RRT will be tabulated by treatment arm (including pooled active treatment arms).

A subgroup analysis will be performed on patients without acute RRT at baseline.

9.3.1.9 Duration of RRT up to Day 90 (excluding patients on RRT for chronic renal failure at time of randomisation)

Duration of RRT is defined as the cumulative periods with RRT (continuous renal replacement therapy, intermittent hemodialysis or peritoneal dialysis) and will be analyzed excluding patients on RRT for chronic renal failure at time of randomisation.

For patients withdrawn or dying while still on RRT, the duration will be based on the data available up until the time of withdrawal or death.

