9.3.4 Fluid Balance

9.3.4.1 Daily and Cumulative Fluid Balance Until ICU Discharge (for a Maximum of 7 Days)

Fluid overload is defined as fluid balance volume (L) as a percentage of baseline weight. E.g. if a patient weighs 90 kg at baseline and has a fluid balance of 9 liters, fluid overload is then 100% * 9L / 90 kg = 10%.

Fluid balance (as a rate of time) and cumulative fluid balance (total volume) will be presented both unadjusted and adjusted for weight.

Baseline fluid balance (as a rate of time) and baseline fluid balance volume (mL) will be based on the time from onset of sepsis induced hypotension to start of IMP.

All analyses will be presented for 'all patients' and for 'patients in ICU throughout Day 0-7'.

Fluid balance, cumulative fluid balance, fluid overload and cumulative fluid overload will all be compared between treatment arms using a repeated measures ANCOVA model with baseline (baseline fluid balance volume (mL) or baseline fluid overload) as covariate, treatment, time and treatment by time interaction as factors, baseline score by time interaction, and patient as the experimental unit. Estimated treatment differences (to placebo) along with a 95% confidence interval will be presented.

Fluid overload and balance will be based on a sectioning of the intervals between the actual sampling time points on baseline, Day 1, 2, etc., in order to be able to make 24 hour intervals from start of IMP.. For Days 1, 2, etc. sampling time points will be every 24 hours from start of IMP. Patients withdrawn or dead will be set to missing.

Endpoints (absolute values and change from baseline) will be tabulated by treatment arm (including pooled active treatment arms), and presented graphically.

Furthermore, in order to assess all patients at Day 3 and 7 (regardless of mortality), the composite endpoint 'critical edema-free survival' will be derived at both Day 3 and 7.

A patient will be categorised as being critically edema-free and alive at Day 3 (or 7 respectively) if:

- fluid overload < 10% at Day 3, or
- patient is discharged from ICU and emergency department prior to Day 3 with a fluid overload < 10% at day of discharge (or previous day if discharged before fluid balance measurement), and patient is alive at Day 3.

The patient will be categorised as not being critically edema free or dead if:

• fluid overload $\geq 10\%$ at Day 3, or

Date: 20 Nov 2017 E-Statistical Analysis Plan-17877; Ver.9.0

Supersedes: Ver. 8.0 Page 38 of 80

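### Creatinine clearance (SAP 9.4.11) has no rule for values taken on renal replacement therapy, so this additional endpoint is biased towards the arm with more RRT started after randomisation

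*SAP*

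**What the plan says.** Section 9.4.11 defines the endpoint by formula: "Creatinine clearance is determined by estimated glomular filtration rate (using creatinine, age, and gender as per Cockcroft-Gault"). The printed equation is (140 − age) × weight / creatinine for women, and "For men, multiply result by 1.2". For the analysis, "Creatinine clearance will be analyzed up until day 3 as for fluid balance in Section 9.3.4.1, with baseline creatinine clearance as a covariate".

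Section 9.3.4.1 supplies a repeated-measures ANCOVA and one rule on patient status: "Patients withdrawn or dead will be set to missing". The population comes from 9.1: "All efficacy endpoints will be analysed for the FAS analysis set", which under 6.2 means everyone randomised and dosed. RRT is mentioned in neither 9.4.11 nor 9.3.4.1.

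Elsewhere the SAP does deal with RRT status. In 9.3.1.7, "RRT-free Days will be analyzed excluding patients on RRT for chronic renal failure at time of randomisation", and 9.3.1.8 and 9.3.1.9 make the same exclusion. Section 9.3.1.8 also expects some patients to enter on acute RRT: "A subgroup analysis will be performed on patients without acute RRT at baseline".

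**The concern.** The formula is inversely proportional to serum creatinine. RRT removes creatinine from the blood, so once it starts the formula returns a higher clearance although the kidneys have not recovered. Followed as written, the SAP enters that number into the model as native renal function.

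Whether patients need RRT after randomisation is itself an outcome that may differ by arm, and the SAP tests it: "Incidence of RRT will be analysed by a logistic regression model with time from onset of shock to start of treatment" and further covariates. If one arm has more early RRT, its mean clearance is raised by the RRT itself. The clearance result could then point the opposite way to the RRT results.

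The SAP guards against this kind of distortion in other places. It counts deaths as RRT in 9.3.1.8, and in 9.3.1.5 it gives patients who die the worst SOFA value. Clearance has no equivalent protection.

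**Working it through.** The SAP states no figure for this endpoint, so there is none to reproduce. The check applies the SAP's own equation to assumed values.

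**Inputs from the SAP:** the equation and the factor 1.2 for men (9.4.11); the window to Day 3 (9.4.11); all FAS patients (9.1); only dead or withdrawn patients set to missing (9.3.4.1).

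**Assumed inputs:** age, weight, creatinine before and during RRT, and the difference in RRT use between arms. That RRT lowers serum creatinine is general knowledge and is not stated in the SAP.

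**Step 1: false gain per patient.** At age 65 and 80 kg, (140 − 65) × 80 = 6000 for a woman, and 6000 × 1.2 = 7200 for a man.

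| Creatinine (µmol/L) | Woman (mL/min) | Man (mL/min) |
|---|---|---|
| 300, before RRT | 20 | 24 |
| 200 on RRT | 30 (gain 10) | 36 (gain 12) |
| 150 on RRT | 40 (gain 20) | 48 (gain 24) |
| 100 on RRT | 60 (gain 40) | 72 (gain 48) |

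**Step 2: shift in the arm mean.** With native function equal in both arms, the shift is (difference in RRT proportion) × (false gain per RRT patient). For gains of 10 to 40 mL/min:

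- 2 points more RRT: 0.02 × 10 to 0.02 × 40 = 0.2 to 0.8 mL/min
- 5 points more: 0.5 to 2.0 mL/min
- 10 points more: 1.0 to 4.0 mL/min

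**Step 3: check with whole-arm means.** Suppose 70% of each arm has clearance 60 and 30% has native clearance 24, reading 48 on RRT. With 30% on RRT the mean is 0.7 × 60 + 0.3 × 48 = 56.4. With 20% on RRT it is 0.7 × 60 + 0.1 × 24 + 0.2 × 48 = 54.0. The difference is 2.4 = 0.10 × 24, although native function is identical.

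**Step 4: what the model sees.** The model adjusts for baseline, so the course from baseline matters. Take a man of 70 years and 80 kg: 70 × 80 × 1.2 = 6720. He enters at 150 µmol/L (44.8 mL/min), worsens to 400 (16.8 mL/min), and is brought back to 150 by RRT (44.8 mL/min). He shows no change from baseline, so a fall of 28 mL/min is hidden. If he had entered at 400, the same treatment would show as a gain of 28 mL/min. Either way his value on RRT is 28 mL/min too high.

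**The case against.** The strongest counter-argument is that this endpoint carries little weight. Section 2.2.5 lists creatinine clearance among the additional endpoints. It is not in the organ-dysfunction list of 2.2.3 and not in the Hochberg family of 9.3, and no success or label claim rests on it. RRT-free days, RRT incidence and RRT duration are reported separately and would show an imbalance in RRT. This stands and limits the consequences. It does not correct the clearance estimate.

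A reader might infer that the patients with the worst renal course contribute the largest apparent gains. The documents do not support that. As step 4 shows, a patient who deteriorates after entry and is then dialysed may show no gain from baseline. A true recovery in the same man from 150 to 80 µmol/L (44.8 to 84 mL/min) would show a gain of 39.2. Any decline recorded before RRT starts also stays in the repeated measures. The error is often masked deterioration.

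A reader might also infer that every RRT patient pushes the comparison the same way. Chronic RRT and acute RRT at baseline precede randomisation and are balanced in expectation. They add noise and distort the baseline covariate. Only RRT started after randomisation and before the Day 3 cut-off drives the directional bias, and the SAP gives no rate for it.

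Finally, a score of 0 mL/min for time on RRT is not the only reasonable remedy. For a patient whose clearance before RRT is 16.8 mL/min, zero imposes a loss of 16.8. At an assumed 5-point excess that is 0.05 × 16.8 = 0.84 mL/min against the arm with more RRT. This stands, so the choice of value needs its own justification.

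**Conclusion.** The gap is real and lies within the SAP, which fixes the derivation, model, population, window and missing-data rule for this endpoint and leaves no rule for values on RRT. Applied as written, it gives values that do not measure native renal function and tilts the comparison towards the arm with more RRT started after randomisation.

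The direction follows from the inverse formula plus the fact that RRT lowers creatinine. The size, about 0.2 to 4 mL/min in the arm mean, rests wholly on the assumed 2 to 10 point excess and the assumed gain of 10 to 40 mL/min. It cannot be set against a standard deviation or a meaningful difference, because the SAP gives neither. It would be wrong to conclude that the trial's renal claims are compromised: those rest on the RRT endpoints. The point is confined to an additional endpoint, but there the rule as written should be changed.

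**What to change.** In 9.4.11:

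1. Exclude patients on RRT for chronic renal failure at randomisation, using the exclusion already in 9.3.1.7.
2. State that creatinine values obtained during acute RRT, at baseline or later, are not used as observed, and define when a value counts as obtained on RRT if sessions are intermittent.
3. Prespecify one handling as the main analysis and the other as sensitivity analysis: values on RRT set to missing, or assigned a prespecified poor value in line with the SAP's worst-value scoring elsewhere.
4. Interpret the result alongside RRT incidence (9.3.1.8).

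The cost is SAP wording and one extra analysis; RRT timing is already needed for RRT-free days and RRT duration. Each handling has a drawback. Setting values to missing loses data from patients with poor renal function, and a patient whose baseline value is removed drops out of a model that adjusts for baseline. A poor value creates a point mass in the outcome, and in the covariate if applied at baseline. Reporting both shows how far the conclusion depends on the choice.
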